### 7.1. Adverse Events Analyses

Adverse events analyses including the analysis of adverse events (AEs), Serious (SAEs) and other significant AEs will be based on GSK Core Data Standards.

### 7.2. Clinical Laboratory Analyses

Laboratory evaluations including the analyses of Chemistry laboratory tests, Haematology laboratory tests, Urinalysis, and liver function tests will be based on GSK Core Data Standards. Other Safety Analyses

The analyses of non-laboratory safety test results including ECGs and vital signs will be based on GSK Core Data Standards, unless otherwise specified.

The immunogenicity of GSK2831781 will be characterized with summary statistics of incidence, i.e. the count of participants with positive confirmed anti-drug antibodies by treatment over time. Immunogenicity testing involves a screening assay and a confirmation assay that together produce three results:

- Screening assay result (binary (yes/no))
- Confirmatory assay result (binary (yes/no))
- Titre result (numeric)

## 8. EFFICACY ANALYSES

Unless otherwise specified, endpoints / variables defined in this section will be summarised by treatment using descriptive statistics, graphically presented (where appropriate) and listed.

Details of the planned displays are provided in [Appendix 12: List of Data Displays](#) and will be based on GSK data standards and statistical principles.

### 8.1. Primary Efficacy Analyses

The primary efficacy endpoint is change from baseline over the induction phase.

#### 8.1.1. Primary Endpoint

The Complete Mayo Score will be analysed with a Bayesian ANCOVA model, using the following estimands.

##### 8.1.1.1. Primary Estimand – Treatment Policy

Primary estimand: “Treatment policy”	
Objective:	To characterise the efficacy of GSK2831781 during the Induction Phase.
Estimand:	
Primary efficacy estimand
 
Description
 
Mean change from baseline to Week 10 in Complete Mayo score for each dose level and placebo in patients with moderate to severe, active Ulcerative Colitis and in the absence of IP discontinuation due to the COVID-19 pandemic.
 
Attributes
 
 
• Treatment: Placebo and four doses of GSK2831781 IV: 450mg, 300mg, 150mg and 45mg in addition to background therapy and stable dose of corticosteroid where relevant.
 
• Population: Patients with moderate to severe, active, Ulcerative Colitis as per inclusion/exclusion criteria.
 
• Outcome measure: Change from baseline to Week 10 in Complete Mayo score.
 
• Intercurrent events and strategy: 
 
• Intercurrent event (ICE): Discontinuations due to the COVID-19 pandemic 
 
◦ Strategy: hypothetical, setting assessments to missing with missing at Random [MAR] assumption.
 
 
 
• ICE: Discontinuations due to sponsor’s decision to terminate the study
 
 
 

Primary estimand: “Treatment policy”	
	
 
○ Strategy: hypothetical, setting assessments to missing with missing at Random [MAR] assumption.
 
● ICE: Discontinuations not due to the COVID-19 pandemic or to sponsor’s decision to terminate the study 
 
○ Strategy: treatment policy (no imputation).
 
 
 
● Population-level summary: Mean change from baseline.
 

Estimation and missing data details for the primary estimand (“Treatment Policy”)	
	Discontinuations due to reasons related to the COVID-19 pandemic or to sponsor’s decision to terminate the study will be handled with a hypothetical strategy; the subsequent assessments will be set to missing in the analysis dataset (even if post discontinuation data is collected).
	Assessments following IP discontinuations for other reasons will be used in analysis.
	In all cases, the missing endpoint will be assumed to be MAR in the statistical analysis.
	The MAR assumption is implicit in the planned Bayesian analysis.

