1.2. Schema

*Randomisation will initially be 2:1 to GSK2831781 450 mg or Placebo. When an appropriate number of participants have been randomised in these two arms for the interim analysis (Interim Analysis 3, see Section 9.5), randomisation to all dose regimens (GSK2831781 450 mg, 300 mg 150 mg, 45 mg or placebo) will be opened at a ratio of 2:3:3:3:2.. Dosing during the Double-Blind Induction Phase will be undertaken at Weeks 0 (Day 1), 2, 6 and 10. Responders at Week 10 (where Responder status is determined by a pre-specified algorithm in the eCRF) will continue into the Double-Blind ETP.

Participants originally randomised to GSK2831781 IV treatment arms (Induction) will receive subcutaneous doses of 300 mg GSK2831781 every 4 weeks at Weeks 14, 18, 22, and 26. Participants originally on placebo treatment arm, who attained response, will continue to receive blinded placebo through SC dosing at Weeks 14, 18, 22 and 26. The Double-Blind ETP ends at Week 30, with Follow-Up until Week 42 (16 weeks after the last dose).

[†]The open label patient journey is described fully in Section 4.1.2 and [Figure 3](#). The Open Label ETP, for Non-Responders at Week 10, will constitute a full 10 weeks of induction dosing according to the same dosing schedule as GSK2831781 450 mg (IV doses at Weeks 12, 14, 18 and 22). The Open Label Induction Phase (OLIP) will start at Week 12 to allow turnaround of centrally determined responder status. Response following OLIP will be assessed at Week 22 in the Open Label ETP, and Responders will continue with doses of 300 mg GSK2831781 subcutaneously every 4 weeks from Week 26 to 38. Participants will then undertake a Follow-Up period of 12 weeks from Week 42 to Week 54. Participants in the Open Label ETP who are Non-Responders at Week 22 will discontinue study treatment and be managed according to physician standard of care but are still required to attend a Follow-Up visit approximately 16 weeks from the last dose event.

1.3. Schedule of Activities (SoA):

Double-Blind Treatment SoA

WEEK	Screening		Induction Phase					Extended Treatment Phase					Follow-Up ²⁰	Early Withdrawal Visit ^{21, 26}		
	Pre-dose	Post-dose	2	4 ²⁶	6	10	12 ¹⁹	14	18 ²⁶	22 ²⁶	26 ²⁶	30	42 ²⁶			
DAY	-35 to -7 ²³	-14 to -7 ¹⁴	Day 1		15	29	43	71	85	99	127	155	183	211	295	
Window (days)					±2	±3	±3	±3	±5	±3	±3	±3	±3	±3	±7	
Study Population																
Informed Consent	X															
Inclusion/Exclusion Criteria	X															
Demography	X															

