- 18 Samples to be taken up to 2 hr before the next dose, and one sample immediately after end of IV infusion (within 15 minutes).
- 19 Week 12 visit scheduled to enable recall of Non-Responders to move to Open Label dosing at Week 12, see Open Label Treatment SoA below. Telephone call can be used to ensure Responders initiate steroid taper and cancel scheduled visit for Responders next due to undertake dosing at Week 14.
- 20 In case of Early treatment discontinuation, or study withdrawal, the investigator should undertake a Follow-Up visit approximately 16 weeks after the last dose event to allow safety monitoring following drug washout.
- 21 Participants who discontinue study treatment are encouraged to complete remaining scheduled visits for the treatment phase they are in. However, an Early withdrawal visit is only required for participants who prematurely discontinue study treatment and do not agree to complete the remaining scheduled visits for that phase.
- 22 Complete 4-domain Mayo Score (including Endoscopy) to be performed if withdrawal from study treatment occurs after Week 4 but prior to Week 10 (all participants) or between Week 18 and Week 30 for Responders. The endoscopy is to be performed either at the Early Withdrawal Visit (for participants who do not wish to complete remaining scheduled visits), or at Week 10 or Week 30 (for participants that agree to complete remaining scheduled visits after withdrawing from treatment).
- 23 The window for Screening Visit 1 can be extended to Day -45 where indeterminate test results are returned for assays requiring long central laboratory turnaround times (e.g., QuantiFERON and *C. difficile*). However, if haematology, clinical chemistry and (if applicable) serum pregnancy tests have been

performed outside of the Day -35 window they must be repeated and recorded as an unscheduled visit in the eCRF to confirm eligibility, even if performed at Screening Visit 2.

- 24 Faecal Calprotectin sample may be taken up to 48 hours prior to scheduled visit.
- 25 Exit interview, if applicable, to be undertaken either at Early Withdrawal or Follow-Up.
- 26 Home health care / telemedicine visits may be permitted where applicable country and local regulations and infrastructure allow.
- 27 Randomisation may be performed on Day -1. Randomisation may only proceed when all information pertaining to patient eligibility has been confirmed, including eCRF Mayo score eligibility calculation.

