4.1.1. Double-Blind Treatment

[figure not shown]
Following informed consent, the screening period for participants is 35 days. Eligible participants, determined by entry criteria including the baseline centrally read endoscopy (endoscopy to be completed no earlier than Day -14), will be randomised on either Day 1 or Day -1, and commence 10 weeks of blinded treatment in the Double Blind Induction Phase (IP).

At Week 10, all participants will undergo an Induction Assessment, including centrally read endoscopy. Following the endoscopy, the Responder status (see [Appendix 7](#), Section [10.7](#)), as identified by the results of the central assessment of clinical response and implemented in the eCRF, will be communicated to sites prior to the Week 12 visit.

Participants identified as Responders who received GSK2831781 during Induction will then receive 300 mg GSK2831781 subcutaneously (SC) every four weeks during the double-blind Extended Treatment Phase (ETP), from Week 14 until Week 26. Responders in the placebo group during Induction will continue to receive placebo SC every four weeks in the double-blind ETP ([Figure 2](#)). A mandatory corticosteroid taper (if applicable) will begin at Week 12, described in Section [6.6.1.1](#).

At Week 30, all participants in the Double-Blind ETP will undergo an Assessment, including centrally read endoscopy. Subsequently, all participants will remain in study, but off treatment, to Week 42 in the 12-week Follow-Up phase.

Figure 2 Double-blind ETP dosing regimen (for Responders only)

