8.2. Efficacy Assessments

8.2.1. Clinical Disease Assessments

8.2.1.1. Mayo Score

Clinical disease assessments will be undertaken using the Mayo Score. Multiple derivations will be calculated (described below) to enable characterisation of disease status, whilst also enabling comparison of disease remission and response with previous clinical studies in UC.

- The Complete 4-domain Mayo Score is a 12-point scoring system where disease is evaluated based on stool frequency, rectal bleeding, physician global assessment (PGA) and endoscopic appearance (with **CCI** [REDACTED] associated with an endoscopic score of **po** [REDACTED]).
- The Adapted Mayo Score is a 9-point scoring system where disease is evaluated based on stool frequency, rectal bleeding and endoscopic appearance (with any **CCI** [REDACTED] associated with an endoscopic score of **CCI** [REDACTED] or **CCI** [REDACTED]).
- The Partial Mayo Score is a 9-point scoring system where disease is evaluated based on stool frequency, rectal bleeding and PGA, but no endoscopy component, and will be used to follow changes in these parameters over the course of the study.

The patient reported outcomes of Stool Frequency and Rectal Bleeding for Mayo scores will be calculated from participant eDiary data. To provide a participant's Mayo score status during study conduct, eDiary data will be transcribed into the eCRF for calculation of the Stool Frequency and Rectal Bleeding subscores. Identification of data to be used for calculation of the Mayo score will be based on:

- 3 consecutive days.
 - Where 3 consecutive days are not available, non-consecutive days may be used.
 - For determining eligibility in Screening, 3 days are mandatory. Exceptionally, for determining Responder status at Week 10 double blind and Week 22 Open Label, 2 days may be sufficient, the RAP details how these participants will be handled in the study analysis.
- Within 7 days prior to the endoscopy.
- As close to the date of endoscopy as possible.
- Excluding any days in which bowel preparations are administered.

For further guidance on which days to select in case of missed eDiary entries in any of the targeted days, see SRM for full details. Note that calculations must be made within eCRF to determine Eligibility (prior to Randomisation) and Responder status.

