## 8.2. Secondary Efficacy Analyses

### 8.2.1. Key Secondary Endpoint

#### 8.2.1.1. Estimand

Key secondary estimand for decision making: "Composite"	
Objective:	To investigate the effect of repeat doses of GSK2831781 on clinical efficacy including endoscopic mucosal healing during the Double-Blind Induction Phase.
Estimand:	
Description
 
Difference in response rates between active doses of GSK2831781 and Placebo when added to background therapy in patients with moderate to severe, active Ulcerative Colitis.
 
Attributes
 
 
• Treatment: Placebo and active doses of GSK2831781 in addition to background therapy and stable dose of corticosteroid where relevant.
 
• Population: Patients with moderate to severe, active, Ulcerative Colitis as per inclusion/exclusion criteria.
 
• Outcome measure: Endoscopic Mucosal Healing at Week 10 assessment, where success is defined as: 
 
○ Achieving a score on the endoscopic component of the Adapted Mayo score of 0 or 1, and
 
○ Not discontinuing IP due to reasons unrelated to the COVID-19 pandemic or to sponsor's decision to terminate the study, and
 
○ Not taking medications excluded by the protocol or increasing dose of corticosteroid.
 
 
 
• Intercurrent events and strategy: 
 
○ ICE: discontinuation from IP, unrelated to COVID-19 pandemic or to sponsor's decision to terminate the study.
 
○ Strategy: included in outcome via composite strategy (i.e. post-ICE result set to non-response).
 
○ ICE: discontinuation from IP, due to COVID-19 pandemic.
 
○ Strategy: hypothetical, setting response status to missing.
 
○ ICE: discontinuation from IP, due to sponsor's decision to terminate the study.
 
○ Strategy: hypothetical, setting response status to missing.
 
○ ICE: valid endoscopy result not available, due to COVID-19 pandemic
 
 
 

Key secondary estimand for decision making: “Composite”	

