## 15.4. Appendix 4: Treatment Phases and Study Phases

### 15.4.1. Treatment Phases

The table below defines treatment phases. Note that if a participant receives study drug at all visits and completes the study, all visits will be categorised as 'on-treatment' including the follow-up visit. Note: follow-up visits for participants who early withdraw in Double Blind Induction and for participants who early withdraw in other study phases without completing all protocol-defined visits in that phase will not be summarised (they will be listed).

Where treatment is discontinued during the study (i.e. the 'study treatment discontinuation' form has been completed in the eCRF), the Study Treatment Stop Date will be defined as the date that the last treatment was given.

Treatment Phase	Definition
Pre-Treatment	Date < Study Treatment Start Date
On-Treatment	Study Treatment Start Date ≤ Date ≤ Study Treatment Stop Date + 16 weeks (+ 7 days, the visit window)
Post-Treatment	Date > Study Treatment Stop Date + 16 weeks

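### After a COVID-19 or termination stop, the SAP blanks a collected Week 10 result even when every dose due before it was given, so estimand-based analyses lose usable data

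*SAP*

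**What the plan says.** SAP 8.1.1.1 handles discontinuation of study drug in two ways. For COVID-19 or termination it is hypothetical, and "the subsequent assessments will be set to missing in the analysis dataset (even if post discontinuation data is collected". For any other reason it is treatment policy: "Assessments following IP discontinuations for other reasons will be used in analysis". The key secondary estimand in SAP 8.2.1.1 lists "discontinuation from IP, due to sponsor's decision to terminate the study" (and, separately, the COVID-19 equivalent) and sets response status to missing. SAP 8.2.2 and 8.2.3 copy these strategies to the other secondary endpoints.

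On timing, Protocol 1.2 states: "Dosing during the Double-Blind Induction Phase will be undertaken at Weeks 0 (Day 1), 2, 6 and 10". Protocol 4.1.1 states: "At Week 10, all participants will undergo an Induction Assessment, including centrally read endoscopy". Protocol 8.2.1.1 takes the diary days for the Mayo score from this period: "Within 7 days prior to the endoscopy".

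For a participant who stops drug after Week 4 and before Week 10, footnote 22 of the double-blind schedule (Protocol 1.3) still asks for the Complete Mayo score with endoscopy. It is done at an Early Withdrawal visit "or at Week 10 or Week 30 (for participants that agree to complete remaining scheduled visits after withdrawing from treatment".

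The SAP gives no rule for dating an intercurrent event. The nearest definition, written for treatment phases in SAP 15.4.1, is that "the Study Treatment Stop Date will be defined as the date that the last treatment was given".

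**The concern.** The hypothetical strategy asks what the Week 10 score would have been had the pandemic or the termination not stopped treatment. When only the Week 10 dose is missed, treatment before the assessment matches that of a participant who continued. If nothing else changed before an on-schedule assessment, the collected score is the best available evidence on that question. The SAP removes it and relies on a missing-at-random assumption.

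The primary model in SAP 8.1.1.2 is a regression on the Week 10 change alone, so a blanked participant adds nothing to the treatment estimate. The same holds for the logistic model of endoscopic healing. At stake is precision in a 450 mg v placebo comparison that early termination has already cut short.

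**Working it through.** **Timing.** With study day = 7 × week + 1 (SAP 15.3.1), doses fall on Days 1, 15, 43 and 71, and the assessment is due on Day 71. From Day 43 to Day 71 (28 days), every dose due before the assessment has been given. SAP 15.4.1 counts as on-treatment anything up to 16 weeks (+7 days) after the last dose. From Day 43 that is Day 43 + 112 = 155, or 162 with the window, so Day 71 is on-treatment by the SAP's own definition.

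**Dating of the event.** If the intercurrent event takes the last-dose date, a participant whose Week 10 dose was withheld is dated Day 43. The Week 10 result is then blanked even if it was obtained on schedule. If the event is dated when the stop was decided, a participant assessed at Week 10 and stopped at that visit keeps the result. The SAP does not say which applies.

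**Which results resemble a continuing participant's Week 10.** For someone who takes no further dose, the Week 10 analysis window (SAP 15.3.1) runs from Day 58 to at least Day 85. That is 58 − 43 = 15 days to 85 − 43 = 42 days after the Week 6 dose, against a planned 71 − 43 = 28. Early Withdrawal visits are slotted by actual date. Falling in the analysis window is therefore too loose a test. The visit window in the schedule, Day 71 ±3, gives 25 to 31 days.

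**Plan's own figure.** No figure in the plan rests on this rule. The nearest is in Protocol 9.2.1: 40 v 20, SD 1.5, difference 2, 90% power at 5%.
- SE = 1.5 × √(1/40 + 1/20) = 0.411.
- Two-sided power = Φ(2/0.411 − 1.96) = 99.8%.

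The stated 90% holds only as a lower bound. This is a separate matter. The percentages below do not depend on the SD.

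**Precision.** The number affected is not given, so take m retained participants per arm on the 40 v 20 base. The SE ratio is √(1/(40+m) + 1/(20+m)) / √(1/40 + 1/20).

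| m per arm | SE (SD 1.5) | change |
|---|---|---|
| 0 | 0.411 | – |
| 1 | 0.403 | −2.0% |
| 2 | 0.395 | −3.9% |
| 3 | 0.387 | −5.7% |

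**Bias.** In 20,000 simulated trials at each of 10%, 20% and 30% loss unrelated to outcome, the mean difference was −2.00 with or without the deleted values. Only the spread changed. This shows no bias under that assumption; it does not test the assumption.

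**The case against.** The strongest reply is that equal doses do not make the period before the assessment equal. A participant taken off drug with active UC may start other therapy before Week 10. The primary estimand has no intercurrent event for prohibited medication, and SAP 2.1.4 removed the hypothetical estimand that covered it. A test on doses alone would bring the effects of such therapy into an estimand meant to exclude the termination. For the key secondary endpoint, SAP 15.6.3.5 lets the earliest event govern. If the discontinuation no longer counted, later medication would turn a sponsor-caused stop into non-response. This objection stands, and the fix must carry a medication condition.

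Other points also stand:
- No section states that the endoscopy precedes the Week 10 infusion. This is inferred from the schedule and from diary days being taken before endoscopy.
- Knowledge of the termination could shift the diary items and the site-reported physician global assessment. Only endoscopy is read centrally.
- Keeping Week 10 values after other discontinuations is the treatment-policy strategy at work, not in itself an inconsistency.
- The values are not lost from reporting. Observed summaries remain (for example Tables 2.2, 2.8 and 2.17), beside the estimand versions.

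A reader might infer that everyone between Week 6 and Week 10 on 14-JAN-2021 was affected. The documents do not support that. It is the date of the decision, and nothing says dosing stopped that day or who attended afterwards. Converting the four-week slice into a head count would also need a recruitment rate, which is not given.

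**Conclusion.** The point holds in a limited form. For a participant with the Week 0, 2 and 6 doses, an on-schedule Week 10 assessment and no new UC therapy, the SAP removes from the estimand-based analyses a result that closely represents the hypothetical outcome. The loss is one of precision: 2.0% to 5.7% in the SE if 1 to 3 per arm were recovered on a 40 v 20 base, and nothing if no such participant exists. Both the base and the numbers recovered are assumptions.

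Two stronger readings are not supported. One is that the rule biases the treatment difference; nothing in the documents shows this. The other is that a hypothetical strategy is wrong for these events. It is legitimate, and setting to missing remains appropriate when an earlier dose was missed because of the stop, the assessment was off schedule, or new therapy intervened.

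**What to change.** In SAP 8.1.1.1 and 8.2.1.1, and so in the endpoints of 8.2.2 and 8.2.3 that copy them:

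1. Define the date of the discontinuation event.
2. After a COVID-19 or termination discontinuation, keep the Week 10 result in the main analysis when all three conditions hold:
   - (a) the Week 0, 2 and 6 doses were given;
   - (b) the assessment was made at the scheduled Week 10 visit, Day 71 ±3;
   - (c) no prohibited or increased UC medication was started between the stop and the assessment.
3. Otherwise, after such a discontinuation, keep set-to-missing. For the key secondary endpoint this includes the case where that medication followed the stop, so that it is not scored as non-response. Participants who did not discontinue for these reasons are unaffected.
4. State in SAP 8.2.1.1 that termination discontinuations with missing results are not counted as non-response. As written, the estimation details count any Week 10 result missing for non-COVID reasons as non-response, which conflicts with the hypothetical strategy for termination.
5. Run the present set-to-missing rule as a sensitivity analysis.

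The cost is a short SAP paragraph, one derivation flag and one extra run. The downside is exposure of the diary items and the physician global assessment to knowledge of the termination, which the sensitivity analysis helps to gauge.

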### 8.1.1.2. Statistical Analysis

Bayesian analysis for continuous endpoint	
Endpoints	Change from baseline in Complete Mayo Score at Week 10
Statistical analysis	Linear regression
Predictors	
 
● TRT = study treatment(categorical)
 
● Advanced Therapy Experience (categorical) (includes interaction with study treatment)
 
● Baseline Complete Mayo (continuous)
 
● Duration of disease, years (continuous)
 

Model	$y_i \sim \text{Normal}(\text{mean}=\mu, \text{SD}=\sigma)$ $\mu = (\text{TRT=Placebo}) \times (\text{Experienced}=Y) \times \beta_1 +$ $(\text{TRT}=450\text{mg}) \times (\text{Experienced}=Y) \times \beta_2 +$ $(\text{TRT=Placebo}) \times (\text{Naive}=Y) \times \beta_3 + (\text{TRT}=450\text{mg}) \times (\text{Naive}=Y) \times \beta_4$ $+ (\text{Duration}^*) \times \beta_5 + (\text{Baseline}^*) \times \beta_6$

Bayesian analysis for continuous endpoint	
Population-level coefficients ( $\beta$ )	
 
• <math>\beta</math> = fixed effects, parameters associated to predictors  <math>\beta_k</math>: non-informative prior distributions,  <math>\beta_k \sim \text{Normal}(\text{mean}=0, \text{SD}=100)</math>
 
• Standard deviation <math>\sigma</math>:  Non-informative prior Gamma distribution (shape=2, rate=0.1) (Chung, 2013)
 

\* Unless otherwise specified the predictors (not including study treatment) will be centred around their estimated mean in the model

Further details of primary analysis	
Model diagnostics and checking	
	
 
• Each chain will initially have length Of 1,000,000, thin of 10 and burn-in length of 50,000.
 
• Chain convergence diagnostics will be saved in HARP (refdata folder) and inspected.
 
• The MCSE will be compared with the standard deviation of the posterior distribution (SD) to ensure that only a fraction of the posterior variability is due to simulation error, i.e., the ratio MCSE/SD should be close to 0.01
 

Model results presentation	

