### 8.2.3. Other Secondary Endpoints - Continuous

The ICE strategy for the Primary Estimand described in Section 8.1.1.1 above will be replicated in the following secondary Efficacy endpoints:

Endpoint	Endpoint name to be displayed for Estimand Analysis
Change from Baseline in Partial Mayo Score at Weeks 2, 4, 6, 10	Secondary – Partial Mayo Score
Change from Baseline in Adapted Mayo Score at Week 10	Secondary – Adapted Mayo Score
Change from Baseline in Adapted Mayo endoscopic score at Week 10	Secondary – Endoscopic Score
Change from Baseline in UCEIS at Week 10	Secondary – UCEIS Total Score

The four estimands in the table above will be summarised in tables.

In addition, a Bayesian repeated measures analysis will be conducted for the Partial Mayo score, the estimand is described below and the analysis details below that.

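### The primary Week 10 Complete Mayo model is in effect a complete-case analysis that ignores the Weeks 2, 4 and 6 scores, so response-related missingness may bias the treatment difference modestly, in either direction

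*SAP*

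**What the plan says.** The primary endpoint in SAP 8.1.1.2 is "Change from baseline in Complete Mayo Score at Week 10", fitted by Bayesian linear regression. The predictors are treatment crossed with advanced therapy experience, baseline Complete Mayo and disease duration, with vague priors. No post-baseline score appears.

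SAP 8.1.1.1 sets scores to missing after discontinuation for COVID-19 or for the sponsor's termination of the study, even where they were collected. For all other discontinuations: "Assessments following IP discontinuations for other reasons will be used in analysis". It adds: "In all cases, the missing endpoint will be assumed to be MAR in the statistical analysis", and "The MAR assumption is implicit in the planned Bayesian analysis".

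Early scores are scheduled. SAP 8.2.3 lists "Change from Baseline in Partial Mayo Score at Weeks 2, 4, 6, 10", but they enter only the secondary repeated-measures model (SAP 8.2.3.1). Footnote 22 of the schedule of activities (Protocol 1.3) also calls for a Complete Mayo with endoscopy when treatment is stopped after Week 4 and before Week 10. SAP 15.3.1 assigns Early Withdrawal visits by actual date, and the Week 10 window opens on Day 58.

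**The concern.** A single-visit regression with vague priors learns nothing from a participant whose outcome is absent. The stated MAR assumption is therefore narrow: within levels of treatment, therapy experience, baseline score and disease duration, participants with and without a Week 10 score must have the same expected outcome.

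That can fail here. Protocol 6.6.3 and 7.1.1 require study treatment to stop when a participant needs rescue or escalated treatment for colitis, and Protocol 7.1 recognises insufficient response as a reason for stopping. Some of these participants may never reach Week 10. Their Partial Mayo scores at Weeks 2, 4 and 6 would carry information on both the dropout and the likely outcome, but the primary model does not use them. A withdrawal Complete Mayo taken before Day 58 is also unused.

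Nothing planned tests the assumption. The frequentist model in SAP 8.1.1.3 conditions on the same kind of baseline variables. The key secondary endpoint makes a different assumption: SAP 8.2.1.1 counts Week 10 assessments missing for reasons unrelated to COVID-19 as non-response. At stake are the location of the primary estimate and some precision.

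**Working it through.** **Inputs from the documents.** SD 1.5, placebo mean change -1, and 68 (450 mg) and 48 (placebo) participants (Protocol 9.2.1); 40 and 20 at Interim Analysis 3 (same section); 15% as the only attrition figure. The documents give no early-to-Week-10 correlation, no dropout by arm and no strength of link between early response and dropout. These are assumptions, shown as ranges.

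**The plan's own figure.** The plan gives no figure for missing-data bias. The nearest is power above 90% for 42 versus 48, a 2-point difference and SD 1.5. The standard error is 1.5 × √(1/42 + 1/48) = 0.317, and 2/0.317 = 6.31. Two-sided 5% power is Φ(6.31 - 1.96) = 0.99999, so the statement holds as a lower bound.

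**Bias formula.** Let Z be the early score standardised within arm (higher is worse), with correlation ρ to the Week 10 change given the model's covariates. Let the probability of a missing Week 10 score be logistic in Z, with odds ratio OR per SD. If m is the mean of Z among those with a Week 10 score, the complete-case mean of an arm shifts by ρ × 1.5 × m. Hence

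bias in (active - placebo) = ρ × 1.5 × (m_active - m_placebo).

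By numerical integration, m at 10%, 15%, 20% and 30% missing is:
- OR 2: -0.0662, -0.0978, -0.1288, -0.1899
- OR 4: -0.1157, -0.1669, -0.2163, -0.3126

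| Missing, active / placebo | OR per SD | ρ = 0.4 | ρ = 0.6 | ρ = 0.8 |
|---|---|---|---|---|
| 10% / 20% | 2 | +0.04 | +0.06 | +0.08 |
| 10% / 20% | 4 | +0.06 | +0.09 | +0.12 |
| 15% / 30% | 2 | +0.06 | +0.08 | +0.11 |
| 15% / 30% | 4 | +0.09 | +0.13 | +0.17 |

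Smallest: 0.4 × 1.5 × (-0.0662 + 0.1288) = 0.038. Largest: 0.8 × 1.5 × (-0.1669 + 0.3126) = 0.175, or 0.17 before the m values are rounded. Benefit is a negative difference, so a positive bias is towards no effect.

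**Other patterns.** These come from a simulation with 1,000,000 per arm, 15% attrition overall, ρ 0.3 to 0.7:
- Same dropout rule in both arms, true difference -2, OR 2 to 4, 50-100% of the effect present early: +0.02 to +0.18.
- Same rule, no true effect: 0.00.
- Dropout linked to early non-response on placebo only (OR 4): +0.09 to +0.21.
- On active only (OR 4): -0.07 to -0.21, which favours the drug.
- Missingness unrelated to response: 0.00.
- Half of the dropouts retrieved at Week 10 (ρ 0.7, OR 4, half of the effect early): the bias falls from +0.09 to +0.04.

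Adding the early score brought the bias to within ±0.006 of zero throughout. This is partly by construction, because dropout was generated from that score.

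**Scale.** The standard error of the difference is 1.5 × √(1/68 + 1/48) = 0.28, or 1.5 × √(1/40 + 1/20) = 0.41. The largest figure in the table is 0.17/0.28 = 61% of the smaller one.

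**Precision.** With 20% missing purely at random, one early score cuts the variance in large samples by about ρ² × 0.20: 3%, 7% and 13% for ρ of 0.4, 0.6 and 0.8. A simulation using Weeks 2 to 6 with 60 versus 30 participants gave 0%, 4% and 13%.

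**The case against.** The plan has real safeguards. Scores after ordinary discontinuations are kept. Participants who stop treatment are encouraged to finish the phase (Protocol 7.1, 7.2). Footnote 22 arranges an endoscopy for many of them, and an Early Withdrawal score from Day 58 can count as Week 10. Open-label treatment follows the Week 10 assessment (Protocol 4.1.2), which gives non-responders a reason to stay. COVID-19 and termination losses may be unrelated to response. Decisions rest mainly on endoscopic healing (Protocol 9.2.1, 9.4.1), and the study was terminated. All of this stands. It limits the size of the problem but does not make the model use the early scores.

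A reader might infer three stronger things that the documents do not support:
- **That discontinued participants are dropped.** SAP 8.1.1.1 says the opposite; only those with no Week 10-window score are lost.
- **That the estimate is biased.** Bias needs response-related missingness that acts unequally on the two arms' means, and its sign depends on which arm loses its non-responders.
- **That no sensitivity analysis touches missing data.** SAP 15.6.3.2 plans one for missing diary days if more than 5% of participants are affected, though it does not address dropout. The hypothetical estimand removed in SAP 2.1.4 was not a check on MAR either; it set more data to missing under the same assumption.

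It is also fair that the remedy replaces one MAR assumption with a weaker one. The early scores cannot help participants who left before giving any.

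**Conclusion.** The point holds in limited form. For participants with no Week 10-window score, the primary analysis is complete-case, with MAR conditional on treatment and three baseline covariates only. Scheduled scores that could relax the assumption are unused, and no sensitivity analysis for dropout is planned.

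Under the assumed correlations and unequal dropout, the bias is about 0.04 to 0.17 points towards no effect. It can run the other way if active-arm non-responders are the ones lost. In every scenario at the 15% attrition figure it stays below one standard error. The sizes rest on assumed correlations, dropout rates and dropout strength; the direction cannot be settled from the documents. This is an inexpensive improvement that should be made, not a flaw that invalidates the analysis.

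**What to change.** - **Primary model:** analyse Week 10 change in Complete Mayo jointly with Partial Mayo at Weeks 2, 4 and 6, or multiply impute it by arm from baseline and those scores. Retain treatment by therapy experience, baseline Complete Mayo and disease duration.
- **Withdrawal scores:** let an Early Withdrawal Complete Mayo taken before Day 58 enter as an auxiliary value, not as the Week 10 value.
- **Hypothetical-strategy events:** for COVID-19 and termination, use scores collected before the event and leave later ones missing, as now.
- **Current model:** keep it as a sensitivity analysis.
- **Delta adjustment:** add a pre-specified range of shifts to the imputed scores, separately by arm, because early scores do not protect against dropout that depends on the unseen Week 10 value. For scale, a 2-point shift (the design difference) applied to 15% of one arm moves that arm's mean by 0.15 × 2 = 0.30.

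The cost is SAP wording and a modest amount of new modelling. The model in SAP 8.2.3.1 cannot simply be reused: it covers Partial Mayo only, omits disease duration and the treatment-by-experience interaction, and Partial Mayo has a different baseline visit (SAP 15.6.3.1). No new data collection is needed.
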